9.5 Halting Rules

9.5.1 Sentinel Subject Halting Rules

If any of these conditions are met, further vaccinations will be halted pending SMC electronic review.

9.5.1.1 If none of the following conditions are met, may proceed to the second sentinel subject:

- Any SAE regardless of the relationship to the study product
- Any laryngospasm, bronchospasm, or anaphylaxis within 1 day after administration of study product that is considered related to study product.
- One Grade 3 unsolicited adverse event that is considered related to study product.

9.5.1.2 If none of the following conditions are met, may proceed to the remainder of the cohort:

- Any SAE regardless of the relationship to the study product
- Any laryngospasm, bronchospasm, or anaphylaxis within 1 day after administration of study product that is considered related to study product.
- Any generalized urticaria after administration of study product that is considered related to study product.

- One Grade 3 unsolicited adverse event that is considered related to study product and not resolved or improved to lower grade within 2 days.
- Same Grade 2 or higher solicited local adverse event in both sentinel subjects that is considered related to study product and not resolved or improved to lower grade within 2 days.
- Same Grade 2 or higher solicited systemic adverse event in both sentinel subjects that is considered related to study product and not resolved or improved to lower grade within 2 days.
- Same Grade 2 or higher laboratory adverse event in both sentinel subjects that is considered related to study product.

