2.1.1 Safety/Toxicology of similar vaccines

The plasmid vector backbone, pWRG7077, has been used in several DNA vaccines, including HTNV and PUUV DNA vaccines and a Venezuelan Equine Encephalitis (VEE) DNA vaccine. In the VEE study, 41 subjects received one or more immunizations and there were no serious or unanticipated safety concerns identified.¹⁵ There were 674 AEs recorded for all subjects over the

course of the study, the majority were local with resolution within 24 hours. Systemic AEs were also generally mild and transient; the only Grade 3 possibly vaccine related AE of severe fatigue resolved within 1 day. This study did report 3 SAEs, all of which were GI-related, occurred in the same patient with a recurrence of known ulcerative colitis and all concluded to be unrelated to the vaccine or study-related procedure.¹⁵

Investigators have previously evaluated plasmid DNA vaccine strategies for hantaviruses in both pre-clinical studies and human trials since 1999.¹⁶ As referenced above, two prior hantavirus DNA vaccine trials have been published in humans. The first involved 3 cohorts of volunteers vaccinated with a DNA vaccine expressing M segments of HTNV and/or PUUV delivered via disposable gene gun devices (a.k.a. particle mediated epidermal delivery, PMED). Among the 28 subjects to receive at least one dose of vaccine, there were no SAEs related to the vaccine or study-related procedures and no subject withdrew due to adverse events.⁴ Injection site pain was noted following 48-56% of doses and injection site tenderness following 79-89% of doses. All injection site pain was mild and moderate tenderness was documented only following the 3rd dose in 7% of subjects. The most common systemic AEs were fatigue, malaise, myalgia and, headache. Less common was oropharyngeal pain noted in 3 subjects. With the exception of one severe headache, all events were graded as mild or moderate in severity.

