The first 24 participants in Cohorts 1 and 2 will include one sentinel subjects in each cohort since this is a first-in-human Phase 1 study. Sentinel subjects will receive 2 mg of study vaccine in an open label manner but will be randomized and blinded to the dose regimen. Subjects randomized to the 3 dose regimen (Cohort 1) will receive ANDV DNA vaccine on Days 1, 29 and 169, and placebo on Day 57. Subjects randomized to the 4 dose regimen (Cohort 2) will receive ANDV DNA on Days 1, 29, 57 and 169. One sentinel subject will be vaccinated, followed for one day for safety and reactogenicity, and if no halting rules are met, then the second sentinel subject will receive study vaccine in an open-label manner. The two sentinels will be followed for safety through Day 8 (laboratory and solicited/unsolicited AEs) and if no pre-defined halting rules are met and no safety concerns are identified, enrollment of the 22 remaining subjects in Cohort 1 and 2 will proceed, otherwise a Safety Monitoring Committee (SMC) meeting will be held to conduct an electronic review (E-Review) of clinical and laboratory safety and reactogenicity data. While safety data is being evaluated for the sentinel subjects, no new subjects will be enrolled, but screening may continue.

The 22 non-sentinel subjects in Cohorts 1 and 2 will be randomized in a 9:2:9:2 ratio (Treatment Arms 1b:1c:2b:2c) to receive either study vaccine (at a dose of 2 mg) or placebo in a 3 or 4 dose

regimen, in double-blind fashion. The SMC will review all available safety data through 7 days post second vaccination for all 24 subjects in Cohort 1 and 2 and provide recommendations to proceed to Cohort 3 and 4 or, if necessary, modify the protocol before proceeding. While safety data is being evaluated by the SMC, no new subjects will be enrolled, but screening for Cohorts 3 and 4 and vaccination of the remaining doses in Cohorts 1 and 2 may continue.

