# All non-sentinel subjects will be blinded to dose and treatment schedule.							
^ 1mg ANDV DNA administered into the left and right deltoid							
+ 2mg ANDV DNA administered into the right and left deltoid.							

As the vaccine is expected to be well tolerated based on previously published studies in humans demonstrating the safety of hantavirus DNA vaccines using the same plasmid backbone, more than one dose will be studied to best investigate safety and immunogenicity.

On vaccination days, all females of childbearing potential will have a urine pregnancy test done. All subjects will have vital signs and a targeted physical examination pre-vaccination. Blood will be collected pre-vaccination for immunogenicity testing. On the first and fourth vaccination days, clinical safety laboratory tests will be collected pre-vaccination. Vaccine and/or placebo will then be administered by intramuscular injection using the PharmaJet Stratis® Needle-Free Injection System, into both the left and right deltoid muscle one after another or simultaneously. In this way, subjects will be blinded to cohort (i.e., dosage group) and treatment arm within a cohort.

Subjects will be observed for 30 minutes after the last injection is given. Reactogenicity will be measured by the occurrence of solicited injection site and systemic AEs. Subjects will maintain a memory aid through 7 days post each vaccination recording temperature, solicited local and systemic symptoms. Unsolicited non-serious AEs will be collected from the time of first study vaccination through approximately 28 days after the last vaccination. SAEs occurring from the time of study vaccination through approximately 6 months after the last study vaccination will be collected. Clinical safety labs will be collected on Days 1 and 169, and 7 days after each vaccination; if labs are outside the clinical laboratory reference range, they will be repeated at the next scheduled visit (sooner if medically indicated) and, followed to normal or stabilization.

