- Grade 3 solicited or unsolicited (clinical sign or symptom) adverse event that occurs in the 7 days following study vaccination, lasts for 24 hours or more without decreasing to a Grade 1 or Grade 2, and does not have an alternative etiology. If the subject has a Grade 3 adverse event as per Reactogenicity Tables 3, 4, 5 or 6 in the seven days following study vaccination and it lasts < 24 hours before decreasing to a Grade 2 or Grade 1 adverse event, see discontinuation criteria for Grade 2 below.
- Grade 3 solicited or unsolicited (clinical sign or symptom) adverse event that occurs >7 days following study vaccination and is ongoing at the time of the subsequent study vaccination (i.e., Day 29, Day 57 or Day 169). Conversely, if this Grade 3 adverse event was resolved or reduced to a Grade 1 or Grade 2 adverse event at the time of the subsequent study vaccination, IP may only be given, following the documented determination by the site principal investigator or appropriate sub-investigator, that it would not render study vaccination unsafe or interfere with the evaluation of adverse events or immunologic response.
- Grade 3 clinical safety laboratory value (according to the toxicity table, Section 9.2.2) that does not decrease to Grade 1 or less prior to the follow-up study vaccination (i.e., Day 29,

Day 57 or Day 169). Any clinical safety laboratory parameter may be re-evaluated only once at the local clinical laboratory to assess eligibility prior to the follow-up study vaccination. If the clinical safety laboratory value decreases to Grade 1 or less, the subject may receive the follow-up study vaccination. The study vaccination should be scheduled to occur within the acceptable protocol-specified window for that visit.

- Subjects who experienced any Grade 2 adverse event that is an unresolved Grade 2 or a Grade 1 at the time of the next vaccination, IP may only be given following the documented determination by the site principal investigator or appropriate sub-investigator, that it would not render study vaccination unsafe or interfere with the evaluation of adverse events or immunologic response.
- As deemed necessary by the site principal investigator or appropriate sub-investigator for noncompliance or other reasons.
- Subject refusal of further study vaccination.
- Termination of this trial.
- New information becomes available that makes further administration of the study vaccine unsafe.

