- Pre-administration systemic reactogenicity assessments will be performed prior to study vaccination to establish a baseline. Subjects will then receive study vaccination via intramuscular injection into the left and right deltoid one after another or simultaneously. The time of administration will be recorded on the appropriate data collection form. Subjects will be observed for at least 30 minutes after the last study vaccination was given. Post-administration local and systemic reactogenicity assessments will be performed. Any AE/SAEs will be recorded on the appropriate data collection form prior to discharge from the clinic.
- Subjects will be provided with a memory aid and other study-related materials to record daily oral temperature, solicited site and systemic AEs, unsolicited AEs, and concomitant medications. Subjects will be encouraged to take their oral temperature around the same time each day. Subjects must not eat or drink anything hot or cold, or smoke within 10 minutes prior to taking oral temperature. Subjects will be instructed on how to use their memory aid and how to measure and record AEs prior to discharge from the clinic. Subjects will be instructed to notify the study center if they develop any severe reactions after study vaccination. If the site principal investigator or appropriate sub-investigator deems the reaction severe enough, further instructions will be given to the subject on the proper course of action, including a return to the clinic for immediate evaluation if appropriate.

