9.5.2 Study Halting Rules

Further enrollment and study vaccinations will be halted for SMC review/recommendation if any of the following are reported:

- Any subject experiences a study product-related SAE from the time of the study product administration through the subject's last study visit.
- Any subject experiences laryngospasm, bronchospasm, or anaphylaxis within 1 day after administration of study product that is considered related to study product.
- Two or more subjects experience generalized urticaria (defined as occurring at more than two body parts) after administration of study product that is considered related to study product.
- Two or more subjects experience a grade 3 unsolicited AE (in the same MedDRA High Level Term) after administration of study product that is considered related to study product and not resolved or improved to lower grade within 2 days.

This trial will also be halted for SMC review/recommendation if, within 7 days after administration of any study vaccination, any of the following occurs:

- Two or more subjects experience the same grade 3 solicited local adverse event that is considered related to study product and not resolved or improved to lower grade within 2 days.
- Two or more subjects experience the same grade 3 solicited systemic adverse event that is considered related to study product and not resolved or improved to lower grade within 2 days.

- Two or more subjects experience the same grade 3 laboratory adverse event that is considered related to study product.

Grading scales for solicited local (application site) and systemic (subjective and quantitative) AEs are included in Section 9.2.2

Grading scales for clinical safety laboratory adverse events are included in Section 9.2.2.

If any of the halting rules are met following any subject receipt of any study vaccination, then this trial will not continue with the remaining enrollments or study vaccinations without a review by and recommendation from the SMC to proceed.

DMID retains the authority to suspend additional enrollment and study interventions/administration of study product during the entire trial, as applicable.

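### The one-day reactogenicity check before the second sentinel dose has no halting criterion that a non-serious, related Grade 3 solicited reaction can meet

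*Protocol*

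**What the plan says.** Protocol Section 4 sets the step: the first sentinel is "followed for one day for safety and reactogenicity, and if no halting rules are met, then the second sentinel subject will receive study vaccine". The same section defines what is being watched: "Reactogenicity will be measured by the occurrence of solicited injection site and systemic AEs". Section 9.1 lists solicited and unsolicited events as separate categories.

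Under Section 9.5.1, meeting a listed condition halts further vaccination until the SMC has done an electronic review. Section 9.5.1.1 lists three conditions for the step between the two sentinels:

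- any SAE
- related laryngospasm, bronchospasm or anaphylaxis within a day of dosing
- "One Grade 3 unsolicited adverse event that is considered related to study product"

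Solicited events enter only later. Section 9.5.1.2, which governs release of the rest of the group, has "Same Grade 2 or higher solicited systemic adverse event in both sentinel subjects that is considered related to study product", with a matching local criterion. Section 9.5.2, for the whole study, has "Two or more subjects experience the same grade 3 solicited systemic adverse event that is considered related to study product", again with a local counterpart. All four carry the further condition of no resolution or improvement in grade within 2 days.

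SAP Section 4 repeats the one-day step and adds no criterion.

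**The concern.** Reactogenicity is half of the stated purpose of the one-day step, yet none of the criteria applied there refers to a reactogenicity event. As written, the second sentinel may be dosed the next day while the first still has, say, a related Grade 3 fever or headache, and no listed rule requires a review first. A related Grade 3 event that happened not to be on the solicited list would require one.

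The product had never been given to humans (Protocol Section 2.3.1). SAP Section 4.3.4 gives 2 mg per vaccination as the highest dose in related hantavirus DNA vaccine studies, so the 4 mg sentinel step goes beyond that experience.

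**Working it through.** **1. Can any rule fire?** Take a non-serious, related Grade 3 solicited reaction in the first sentinel, assessed at one day, and test it against each provision that might stop the second dose.

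| Provision | What it needs | Met at one day? |
|---|---|---|
| 9.5.1.1, SAE | A serious event | No, by premise |
| 9.5.1.1, airway events or anaphylaxis | One of three named events, none on the solicited list | No |
| 9.5.1.1, Grade 3 event | An unsolicited event | No; the same reaction classed as unsolicited would meet it |
| 9.5.1.2, solicited local and systemic | Same event, Grade 2 or higher, in both sentinels; 2 days without improvement | No |
| 9.5.2, solicited local and systemic | Same Grade 3 event in at least two subjects; 2 days without improvement | No |
| Section 4, absence of safety concerns | Both sentinels followed through Day 8 | Too late: second sentinel already dosed |
| 5.4.3, discontinuation | Concerns that subject's own later doses | Does not govern the second sentinel |
| 9.6.2, Medical Monitor's power to stop | An event that meets the halting criteria | No |

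So 0 of 3 criteria in 9.5.1.1 can be met. All 4 solicited criteria elsewhere need two subjects and 2 days. At 2 mg only one subject has been dosed. At 4 mg an earlier 2 mg subject could supply the second case for 9.5.2, but the 2-day condition still cannot be judged at one day.

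What remains is discretionary: 9.5.1.1 permits but does not oblige the next dose, the sponsor may suspend dosing (9.5.2), and the investigator or sponsor may request an ad hoc SMC meeting (9.6.2).

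**2. Exposure.** One second sentinel at each of two dose levels: 2/48 = 4.2% of subjects.

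**3. How often would an added criterion cause a pause?** The plan states no rate for this, so what follows is an assumption built on Protocol Section 2.1.1.

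- Subjects in the three same-backbone trials: 28 (particle-mediated delivery) + 31 (electroporation) + 41 (Venezuelan equine encephalitis vaccine) = 100.
- Severe events of a solicited type: two. In the last of these trials, "the only Grade 3 possibly vaccine related AE of severe fatigue resolved within 1 day". In the particle-mediated trial there was one severe headache, with duration and relatedness not given.
- Neither can be counted in or ruled out. Resolving within a day does not show that the fatigue was below Grade 3 at a check about 24 hours after dosing. The qualifying count x is therefore 0, 1 or 2.

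With p = x/100 for each first sentinel, the chance of at least one pause over two dose levels is 1 − (1 − p)². The upper limit puts the exact (Clopper-Pearson) 95% upper limit for p through the same formula.

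| x | p | Chance of at least one pause | Upper limit for p | Upper limit for the chance |
|---|---|---|---|---|
| 0 | 0% | 0% | 3.6% | 7.1% |
| 1 | 1% | 1 − 0.99² = 2.0% | 5.4% | 10.6% |
| 2 | 2% | 1 − 0.98² = 4.0% | 7.0% | 13.6% |

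The rate could be off in either direction. Those trials counted all doses and full follow-up and used other delivery methods. Against that, 4 mg exceeds the 2 mg maximum in the related hantavirus trials, and Protocol Section 2.3.1 reports more local reactogenicity with this device than with needle and syringe.

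**The case against.** The strongest defence is that the omission is deliberate. Section 9.2.2 treats reactogenicity events as common and known for this type of vaccine, so the protocol acts on an unexpected Grade 3 event in one person but on expected reactions only when they recur. With one subject dosed, a recurrence rule cannot fire. The added criterion would also protect one further subject more strictly than the next 22: a lone Grade 3 solicited reaction in the second sentinel still meets no listed rule.

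The recurrence logic is sound for 9.5.1.2 and 9.5.2 and is not disputed here. It does not fully explain 9.5.1.1. Section 4 makes reactogenicity part of this particular check. The drafters also wrote a stricter single-subject trigger there than in 9.5.1.2, by dropping the 2-day condition for unsolicited events. And before the next 22 subjects, Section 4 asks whether there are any safety concerns; the one-day step has no such clause.

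Three practical objections stand:

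- The criterion is stricter than Section 5.4.3 in nearly every case. That section acts on a "Grade 3 solicited or unsolicited (clinical sign or symptom) adverse event that occurs in the 7 days following study vaccination, lasts for 24 hours" as a minimum, and a reaction seen about 24 hours after dosing has usually lasted less than that. It also serves another purpose, namely re-dosing the same person. A reader might infer that 9.5.1.1 contradicts 5.4.3; it does not.
- Section 7 and Appendix A schedule no contact between Day 1 and Day 8, so the criterion alone would have no defined occasion on which to be applied.
- Discretion is real. Section 7.2 states: "Subjects will be instructed to notify the study center if they develop any severe reactions after study vaccination". The investigator and sponsor can then act.

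**Conclusion.** The gap is real and narrow. At the one-day step no listed rule requires a pause for a non-serious, related Grade 3 solicited reaction. Reactions that qualify as SAEs are caught. The size is 2 of 48 subjects, and the low prior rate means the gap would seldom matter. The pause probability of 0% to 4.0% rests on carrying over a rate from trials with different delivery and counting.

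A reader might infer that the second sentinel had to be dosed whatever happened to the first, or that someone was in fact put at risk. The documents support neither. Proceeding is permitted rather than required, and the sponsor and SMC routes stay open. SAP Section 4.3.3 describes the sentinel steps at both dose levels as complete, citing no safety concerns for Cohorts 1 and 2. An amendment to this trial would now change nothing. The point applies to the protocol as designed and to any later protocol that reuses its text. It is a cheap, optional improvement.

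**What to change.** Add a criterion to 9.5.1.1: *One Grade 3 solicited systemic adverse event, or one Grade 3 solicited local adverse event other than skin discoloration, judged related to study product and not improved to a lower grade by the one-day follow-up.* Discoloration is left out because its Grade 3 is defined by appearance alone.

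State in Section 7 or Appendix A the Day 2 contact with the first sentinel at which grade and relatedness are recorded. Section 4 already plans the one-day follow-up, so this only gives it a place in the schedule.

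The cost, had it been done before enrolment, is a short amendment with IRB approval and at most one extra SMC electronic review per dose level. The price is some strictness: a reaction that would have faded by 24 hours from onset could still delay the second sentinel until the SMC has looked at it.

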9.5.2 Study Halting Rules

Further enrollment and study vaccinations will be halted for SMC review/recommendation if any of the following are reported:

- Any subject experiences a study product-related SAE from the time of the study product administration through the subject's last study visit.
- Any subject experiences laryngospasm, bronchospasm, or anaphylaxis within 1 day after administration of study product that is considered related to study product.
- Two or more subjects experience generalized urticaria (defined as occurring at more than two body parts) after administration of study product that is considered related to study product.
- Two or more subjects experience a grade 3 unsolicited AE (in the same MedDRA High Level Term) after administration of study product that is considered related to study product and not resolved or improved to lower grade within 2 days.

This trial will also be halted for SMC review/recommendation if, within 7 days after administration of any study vaccination, any of the following occurs:

- Two or more subjects experience the same grade 3 solicited local adverse event that is considered related to study product and not resolved or improved to lower grade within 2 days.
- Two or more subjects experience the same grade 3 solicited systemic adverse event that is considered related to study product and not resolved or improved to lower grade within 2 days.

- Two or more subjects experience the same grade 3 laboratory adverse event that is considered related to study product.

Grading scales for solicited local (application site) and systemic (subjective and quantitative) AEs are included in Section 9.2.2

Grading scales for clinical safety laboratory adverse events are included in Section 9.2.2.

If any of the halting rules are met following any subject receipt of any study vaccination, then this trial will not continue with the remaining enrollments or study vaccinations without a review by and recommendation from the SMC to proceed.

DMID retains the authority to suspend additional enrollment and study interventions/administration of study product during the entire trial, as applicable.

